A trained Brown University research team member will call the interested participants, screen participants, complete an informed consent process, and complete the interview all over the telephone. The interviews will be scheduled at a time of each participant's choosing to ensure privacy and convenience. Interviews will be designed to collect information about participants' experiences receiving, preparing, and eating meals; their interaction, if any, with the person who delivers their meals (i.e., driver or mail carrier); and their satisfaction with the meal services. Interviews will be tailored around the needs of older adults with AD/ADRD. If the interviewee loses his or her train of thought, the interviewer will repeat the last topic or sentence. If participants are too impaired to correctly or effectively answer specific questions, the interviewer will use examples rather than open-ended questions.

In addition to the interview questions, we will conduct a brief cognitive assessment (i.e., Telephone Interview of Cognitive Status (TICS-M)) to estimate the participant's level of cognitive impairment. The TICS-M will be conducted after the interview questions, and the score will be used to understand how experiences may differ for clients with differing levels of cognitive impairment. There is no cut-off score on the TICS-M for conducting the interview and it will not affect eligibility. Scores on cognitive screeners, like the TICS-M, do not consistently predict capacity to consent to research and clinical interview is considered the gold standard for capacity assessment. That is why we are using a study-specific capacity to consent assessment and not the score on the TICS-M.

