Enrolling Persons with ADRD on MOW Programs' Waiting Lists to Receive One of the Two Types of Meals. We will work with programs during this pilot research award to test the procedures for enrolling persons with ADRD who are on programs' waiting lists to receive one of the two types of meals that are currently provided by home-delivered meals programs (i.e., meals delivered multiple times a week by the MOW programs versus frozen, drop-shipped meals) As a note: we have been informed by the MOW programs that the frequency of the daily delivered meals has been shifted to multiple times a week due to the COVID-19 pandemic. These meal recipients are still receiving the same number of meals, but delivery may occur multiple times a week instead of daily. Daily meal delivery may resume when the MOW programs are able to safely do so. Both types of meals are regularly provided to individuals with dementia. To do this, the MOW program will identify individuals who are already on their waiting list and during the initial intake indicated that a doctor or other healthcare professional had indicated that they suffer from memory loss, cognitive impairment, any type of dementia, or Alzheimer's disease (this could be self-reported or by the person making the referral). This information is available in the programs' intake records and therefore will not require any additional data collection or screening procedures. Brown University will randomize those individuals into one of the two groups (meals delivered multiple times a week by the MOW programs or frozen meals) and notify the MOW program. The MOW programs will reach out to individuals and offer them the delivery type. If an individual agrees to come off of the waiting list, they will begin receiving meals. If not, they will remain on the waiting list (i.e., there is no penalty for declining). The MOW program will inform the individual that their decision to come off the waiting list will not influence their place on the waitinglist -- that is, if (for whatever reason) decide not to continue to receive their randomly-assigned mealtype, the individual will be returned to the waiting list and will not lose their spot. We are requesting a waiver of informed consent for this portion of the study, as we believe this study meets the five criteria for a waiver as described in 45 CFR §46.116 f 3 (i-v) and detailed below. For those who have agreed to receiving one of the two types of meals, MOW will send client intake information that they regularly collect (e.g., name, address, phone number, date of birth, last four of SSN, race, gender, living arrangement) to Brown University through secure methods. Brown University researchers will randomize the participants and will communicate assignments back to the MOW programs. Upon receiving the assignment, the MOW program will begin service for clients and continue to serve the assigned meals for six months. Following the six-month study period, individuals may continue to receive their assigned meals or roll onto the MOW programs' usual service (i.e., meals delivered multiple times a week by the MOW program). Importantly, the three programs who are participating have agreed to continue to serve meals to interested individuals after the study period ends.

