The research team members conducting the interviews (i.e., [name], [name], [name]) will identify and make note when the content provided by the participant does not contain information pertinent to the questions being asked. As long as the person with dementia participating in the interview is not distressed and wants to continue, then the interview will be completed as planned. In our experience, a participant may understand a question later in the interview and be able to provide relevant information even in cases where they had a less reliable response to an earlier item / interview question. However, if the participant is not able to meaningfully respond to a series of questions such that a lack of data integrity is clear the interviewer can end the interview early. If that occurs, the research team member will end the interview by thanking the participants for their contribution (e.g., "Thank you for sharing that with me. That is all of the questions that I have for you today. I really appreciate you taking this phone call. Is there anything else that you want me to know?"). It is not necessary to tell participants the interview is being discontinued, in all cases empathy and dignity will be prioritized.

For caregivers, interview inclusion criteria consist of being an informal caregiver of a PWD who is receiving home-delivered meals and English-speaking.

4. Recruitment Methods

Randomization to Meal Group: MOW program staff will identify individuals on their existing waiting lists who are age 66+ years and have a self-reported memory impairment or diagnosis of dementia. This information is available in the programs' intake records and therefore will not require any additional data collection or screening procedures.

Brown University will randomize individuals into one of the two groups (meals delivered multiple times a week by the MOW program or frozen meals) and notify the MOW program. The MOW programs will reach out to individuals and offer them the delivery type, allowing them to come off the waiting list. However, participation is voluntary and if individuals do not want to come off of the waiting list, they will retain their place on the waiting list. The MOW program will inform the individual that their decision to come off the waiting list will not influence their place on the waiting list - meaning, if they decide not to continue to receive their assigned meal type, they will be returned to the waiting list and will not lose their spot.

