The average time that clients spend on a waiting list at these three programs is between 3-5 months; individuals who decline to participate or who decide to leave the study and return to the waiting list will keep their original place on the waiting list (i.e., their accrued waiting time). The client information will be shared with the research team at Brown University who will be responsible for randomizing the client to meals delivered multiple times a week by the MOW program or bi-weekly, drop-shipped meals, and communicating the assignment back to the MOW program. We will consult with participating programs, our expert ethicist consultant, [name], RN, JD, and the Brown IRB on the process (e.g., general barriers to enrollment, reasons for refusal). Based on this feedback, we will make refinements to the implementation strategy and training materials for the larger trial.

Brown has an established collaborative relationship with MOWA, which represents over 5000 home-delivered meals programs. In partnership with MOWA, we have already recruited 2 MOWA member programs to participate in this pilot (please see letter of support from MOWA). MOWA's member programs have agreed to collectively enroll clients with ADRD, to devote staff to implement the intervention, and to work with the Brown research team to develop and execute secure data transfer protocols. MOWA has ensured their support of recruiting additional programs to participate, if needed.

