Clients from MOW program waitlist enroll to receive either drop-shipped meals or meals delivered by the MOW program multiple times a week. Those who enroll are randomly assigned meal type delivery. Those who do not enroll remain on the MOW waitlist. Client data will be shared with the research team.	We will enroll 235 clients at 3 MOW program sites (Including a range of 45-60 clients in Florida, 75-80 in Dallas, Texas, and 100-115 at MOW-SanAntonio, for a grand total of 235 participants) who meet the following eligibility: 
• Age 66 years or older• Currently on MOW waitlist• Self-report dementia diagnosis or cognitive impairment	Request waiver of Informed Consent	Request waiver of HIPAA authorization requirement
Client telephone interviews (recorded) 30 minutes	Sub-group of enrolled clients participating in the Pilot. Total number interviews: 6-30 clients from 3 MOW program sites (2-10 clients per site)	1. Requesting a waiver of documentation of Informed Consent 2. Participant Welcome Letter, Participant Consent Form and Consent Checklist (including consent to audio recording) will be used for consent discussion	n/a (no protected health information is collected)

Brown University Informed Consent and HIPAA Authorization, by Subject Group

Brown University IRB Original Approval 02/22/2021

Brown University IRB Amendment Approval 05/11/2021

Brown University IRB Amendment Approval 08/19/2021

Brown University IRB Amendment Approval 10/06/2021

Caregiver/Emergency Contact interviews (recorded) 30-45 minutes	
Sub-group of caregivers or emergency contacts of enrolled clients participating in the Pilot.
 
Total number interviews: 6-30 caregivers/emergency contacts from 3 MOW program sites (2-10 interviews per site)
	
 1. Requesting a waiver of documentation of Informed Consent 2. Caregiver Welcome Letter and Caregiver Consent Form (including consent to audio recording) will be used for consent discussion 	n/a (no protected health information is collected)
---	--	---	--

Brown University Informed Consent and HIPAA Authorization, by Subject Group

Brown University IRB Original Approval 10/22/2021

Brown University IRB Amendment Approval 05/11/2021

Brown University IRB Amendment Approval 08/19/2021

Brown University IRB Amendment Approval 10/06/2021

3) CONDUCT INTERVIEW QUESTIONS

1. Tell me what it's like for [enter name of participant] to get meal deliveries.

Probes:

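### The protocol gives two incompatible orders for randomization and agreement, and does not say whether people randomized before the offer who then decline are linked or analyzed as assigned

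*Combined protocol and SAP*

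**What the plan says.** **Randomize, then offer.** In Part III, section 2, the paragraph on enrolling people from the waiting lists says that staff identify eligible people from intake records and that "Brown University will randomize those individuals into one of the two groups". The program is notified, and then "The MOW programs will reach out to individuals and offer them the delivery type". Anyone who does not accept stays on the list. Part III, section 4 (Randomization to Meal Group) repeats this: "Brown University will randomize individuals into one of the two groups", after which programs "offer them the delivery type, allowing them to come off the waiting list".

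**Agree, then randomize.** Later in the same section 2 paragraph: "For those who have agreed to receiving one of the two types of meals, MOW will send client intake information". It continues: "Brown University researchers will randomize the participants and will communicate assignments back to the MOW programs". Service starts once the assignment arrives. The table of consent and HIPAA authorization by subject group agrees: "Those who enroll are randomly assigned meal type delivery".

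**Either.** A further sentence in section 4 says: "The client information will be shared with the research team at Brown University who will be responsible for randomizing the client". This fits both orders, because Part V, section 4 and Part VI, section 2 say that identifiers are needed to randomize at all.

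**Decliners.** They keep their waiting-list place and accrued time (Part III, sections 2 and 4), and reasons for refusal are a topic for consultation (section 4).

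**The 235.** Part III, section 3 describes 235 people to whom meals will be delivered and treats receiving meals as enrollment. The subject-group table speaks of enrolling 235.

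**Analysis.** The only between-arm comparison stated for the pilot is an exploratory one of nursing home placement between the two groups (Part III, section 2, data linkage). No analysis population is defined.

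**The concern.** Enrollment is the first of the procedures that the pilot is meant to validate (Specific Aims). If the order is unclear, or differs between sites, the pilot cannot say which procedure it tested.

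The order also matters statistically. When agreement precedes randomization, refusal of the initial offer cannot depend on the arm. When randomization precedes the offer, the client and the program staff know the arm when acceptance is decided. A comparison restricted to acceptors then drops people after assignment, possibly different kinds of people in each arm. The protocol itself gives reasons why acceptance might depend on arm: the background says that handling boxes of frozen meals may be hard for people with dementia, and the risk section says that some may strongly prefer one type. The planned follow-on trial of 2300, whose primary outcome is time to nursing home placement (Part IV, waiver criterion ii), would inherit the procedure.

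**Working it through.** **The stated size.** The site ranges in the subject-group table are 45–60, 75–80 and 100–115. The lower ends sum to 45 + 75 + 100 = 220 and the upper ends to 60 + 80 + 115 = 255. The total of 235 lies inside that range (for example 60 + 75 + 100 = 235). It is a feasibility target with no error rate, power, effect size or decline rate behind it, so there is no power calculation to reproduce.

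**The places side by side.**

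| Place | Step 1 | Step 2 | Arm known when the person decides? |
|---|---|---|---|
| Part III, section 2, first half of the enrollment paragraph | Randomize | Offer assigned type | Yes |
| Part III, section 4, Randomization to Meal Group | Randomize | Offer assigned type | Yes |
| Part III, section 2, second half of the same paragraph | Agree, send data | Randomize | No |
| Subject-group table | Enroll | Randomize | No |
| Part III, section 4, later sentence | Share data | Randomize | Not stated |

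A person cannot be randomized both before and after agreeing, so the first two rows conflict with the next two. All are current text.

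**What follows for someone randomized who then declines.**

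1. *Counted in the 235?* Section 3 equates enrollment with receiving meals, so by implication no. That also reconciles section 3 with the table.
2. *Linked to Medicare data?* Not stated. Intake data transfer is described for those who agreed, but identifiers are needed to randomize, so under randomize-then-offer the university would already hold some data on decliners.
3. *Analyzed as assigned?* Not stated.

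**What bias would depend on.** Suppose that neither meal type nor refusal changes placement risk, so everyone randomized has mean risk p in both arms. In one arm let a proportion d decline, with mean risk q among them. Then:

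- risk among acceptors = (p − d·q) / (1 − d)
- departure from p = d·(p − q) / (1 − d)

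The acceptors-only difference between arms is the frozen-arm departure minus the delivered-arm departure. It is zero if nobody declines, if decliners carry average risk, or if the two departures are equal. Its sign depends on which arm loses more people and on whether they are at higher or lower risk. The documents give no value of d, q or p for either arm. Analyzing everyone randomized compares p with p, a difference of zero.

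**The case against.** Much can be said for the plan. The aim is procedural and the placement comparison is exploratory. The university performs randomization under both descriptions, decliners lose nothing on the waiting list, and refusal reasons are to be reviewed. The risk section says that any meals are preferable to none, so declining may be uncommon. The second half of the section 2 paragraph might be a loose recap of the first. Recruitment scripts, a listed attachment not fully in the supplied text, may settle the order in practice. These points limit the likely damage. They do not remove the conflict, because the subject-group table states agree-then-randomize independently of that paragraph.

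Three stronger readings are tempting and are not supported:

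- *That there is no rule for counting the 235.* Section 3 treats receiving meals as enrollment, which largely answers this; the rule only needs to be made explicit.
- *That decliners' data are lost by default.* This is an inference from the sentence on data transfer, and it sits badly with the statements that identifiers are needed to randomize.
- *That the pilot comparison is biased by a known amount or in a known direction.* Any figure would rest entirely on assumed decline rates and risks.

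The choice between the two orders is also partly a preference: randomize-then-offer is equally present in the text, and either order, consistently worded, would end the contradiction.

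**Conclusion.** The contradiction stands with high confidence, since it can be read directly from the text. For people randomized before the offer, the supplied text lacks a rule on linkage and on the analysis set; unsupplied attachments could contain one. The consequence is conditional: bias arises only if randomize-then-offer is used, the comparison is limited to acceptors, and acceptance differs by arm in a way related to placement risk. Its direction and size cannot be estimated from the documents. This should be fixed because the pilot exists to establish the enrollment procedure for the larger trial, not because of any demonstrated error in a pilot result.

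**What to change.** 1. Reconcile Part III, sections 2 and 4 and the subject-group table to one order. Preferably: the program offers to take the person off the list to receive meals by one of the two routes; the person agrees or stays on the list; intake data are sent; the university randomizes; the assignment is released. This order is already in the protocol and makes initial acceptance independent of the arm. Word the offer as a plain service offer with no capacity or comprehension test, so that it stays within the waiver reasoning in Part IV.
2. Apply this going forward only. The October 2021 amendment approval indicates that meals were already being received.
3. State that the 235 counts people receiving meals, consistent with Part III, section 3.
4. State that everyone randomized is analyzed by assigned arm, including those who later return to the waiting list.
5. For anyone randomized before the offer, record the order used, the arm, and acceptance or refusal with the reason. Review acceptance by arm, and report it only as the suppression rule for counts under 11 allows (Part V, section 4, Protections Against Risk; CMS data use agreement, section 9).
6. Link decliners only if the waivers and the data use agreement cover them. The table describes the waivers for clients who enroll, and section 4 of the agreement limits data to the fewest individuals needed. Otherwise label the placement comparison as acceptors only.

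**Cost.** An IRB amendment, wording changes and a short offer script; no extra participants. If sites have been randomizing first, the pilot will contain two procedures, hence the record of which was used. Refusals after assignment will dilute the as-assigned comparison somewhat. Keeping randomize-then-offer with a log would also end the contradiction, but acceptance would still be decided with the arm known.

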Participant incentives are included for persons with dementia and caregivers who are participating in the telephone interviews in the study. Persons with dementia will be mailed a \$50 pharmacy gift card for a 30-minute telephone interview, an amount that is typically offered for interview studies in populations with, or at risk for AD/ADRD. Caregivers will be mailed a \$50 pharmacy gift card for a 30-45-minute telephone interview.

6. Potential Research Risks / Discomforts to Participants.

In order to approve the research, the IRB must consider the risks posed to participants by the research and any efforts to mitigate those risks. The IRB needs to determine that the risks have been both minimized and are reasonable in relation to the anticipated benefits to participants, as well as to the importance of the knowledge that may be gained. The IRB will also consider whether the informed consent process provides potential participants with an accurate and fair description of the risks or discomforts.

The pilot is considered a minimal risk study. Potential risks to individuals receiving meals include mild distress due to not receiving the preferred type of meal. While both options (i.e., meals delivered multiple times a week by the MOW program vs. frozen, mailed meals) are preferable to no meals at all, some participants may have a strong preference for one over the other and experience disappointment if randomized to the non-preferred option. However, given that participants will have expressed an interest in receiving meals and are on the waiting list, receiving any meals will be preferable to receiving none.

There is also a risk of breach of confidentiality to individuals receiving meals and those participating in interviews. The risk of breach of confidentiality will be minimized to the greatest extent possible by the stipulations set forth in the Data Use Agreement with CMS, as well as by the measures described below.

Protecting Participant Data

One risk of the study is a breach of confidentiality with the use of identifiable data. All research staff involved in the study will receive training in the protection of human subjects. The procedures described here address our efforts to minimize the risk of breach of confidentiality. All data management and analyses will be conducted by the Brown Center for Gerontology & Healthcare Research, leveraging its administration and computing infrastructure. Researchers and staff have many years of experience working with identifiable data files on a large scale and have numerous security measures in place to ensure the integrity and confidentiality of the data. CMS data will be covered under the strict terms of a data use agreement (DUA). At the conclusion of this study, or by the date of retention identified in the DUA, a CMS “Certificate of Disposition” certifying the proper destruction of all data obtained from CMS will be sent to CMS. All non-CMS data will be handled in a similarly restrictive manner. In addition, all output containing individual identifiable information is treated as confidential data. This information is never transferred electronically via email.

Identifiable information will not be attached to any research documents, and all data will be identifiable only using the unique identifier specific to this study. All members of the research team have experience collecting data from participants and using secondary data that contains private health information. None of the study team members have had a breach of confidentiality associated with their research.

For participants with dementia and caregivers taking part in the interviews, they may experience some discomfort in responding to the interview questions as they may bring up unpleasant feelings or memories (for example, what things were like before they began receiving meals). However, these risks do not exceed those of topics considered in everyday life and are minimal. In order to protect against these risks, the researchers will remind participants that they are free to stop the interview and recording at any time and it will not impact the receipt of meals. The interviewers will also offer participants to take a break during the interview if there is any indication that the interview becomes too difficult or uncomfortable.

The justification for including persons with dementia and their caregivers in this study is the scientific value of understanding how home-delivered meals help people with dementia, who make up approximately 30% of all MOW clients. Given this population’s unique needs, it is not possible to conduct informative research for this research with other populations (i.e., we have selected this population for scientific reasons; it is not a convenience population). In sum, this

population is being enrolled because the findings of the research will directly inform the delivery of services to people with dementia in the future – and is needed to improve service quality for this population in support of their goal of living independently in the community.

7. **Potential Benefits of the Research. NOTE: Compensation for participation is not a benefit and should not be included in this section.** *In order to approve this research, the IRB must determine that the potential benefits to research participants are reasonable in relation to the potential risks. Very often, research at Brown does not include potential direct benefits to participants, but may only benefit society as a whole by helping researchers.*

Older adults with dementia on MOW waiting lists who agree to participate will receive meals, as opposed to remaining on the waiting list to receive meals. Further, this study would provide information that would assist healthcare systems, providers, payers, programs, persons with dementia, and their caregivers. The minimal risks to subjects are reasonable for the importance of the information that will help understand the comparative effectiveness of the two predominant forms of meal delivery for persons with dementia.

For individuals participating in interviews, they will not directly benefit from being interviewed. However, their participation will help us better understand the experiences of older adults with dementia who receive home-delivered meals.

PART IV. INFORMED CONSENT

Informed consent is a *process*, not just a form. The IRB must ensure the informed consent process clearly discloses and facilitates the understanding of all information needed to make an informed decision to participate while promoting the voluntariness of participation.

Please use the Brown [consent / assent templates](#) and related guidance on the HRPP Forms & Templates page to develop your consent forms.

1. Describe the informed consent process

Telephone Interviews with Participants: One day prior to the scheduled telephone interview, the project coordinator will confirm the appointment with the participant via phone call, email, or text message according to the participant's preference. At the beginning of the telephone interview, co-investigators [name] [name], and/or [name] will review the study procedures and will go over the consent form with study participants, reviewing the form with them and periodically asking them questions about the consent process to be sure that they understand what they are consenting to. (Please see the interview guide for additional information.) [name], [name], and [name] have years of experience conducting research interviews, including interviews with vulnerable populations such as those with cognitive impairment. Nonetheless, [name], [name], and [name] will participate in training by [name], a study Co-I and geriatric psychologist, who has extensive research experience consenting and conducting research interviews with individuals with memory impairment. [name], [name] and [name] will answer any questions the participant might have and remind them that they may opt out of the interview at any time. If a participant agrees to be interviewed, they will give verbal consent to participate that will be recorded by the Brown researcher. The consent forms will address audio recording consent. Participants who decline audio recording may still participate in the interview. In their case, a research team member will take notes during the interview. While the informed consent document will be sent with the welcome letter, a second blank copy of the informed consent form will be mailed to the participant within one week if they request. The consent form will have contact information for both the study PI and the Brown University IRB if they have any questions or concerns. Because interviews will be conducted by telephone rather than in-person, we will seek a waiver of documentation of informed consent.

Telephone Interviews with Caregivers: One day prior to the scheduled telephone interview, the project coordinator will confirm the appointment with the caregiver via phone call, email, or text message according to the caregiver's preference. At the beginning of the telephone interview, the trained research team member will review the study procedures and will go over the consent form with caregivers, reviewing the form with them and periodically asking them questions about the consent process to be sure that they understand what they are consenting to. (Please see the interview guide for additional information.) This research team member will also answer any questions the caregiver might have and remind them that they may opt out of the interview at any time. If a caregiver agrees to be interviewed, they will give verbal consent to participate that will be recorded by the Brown researcher. The consent forms will address audio recording consent. Caregivers who decline audio recording may still participate in the interview. In their case, the research team member will take notes during the interview. While the informed consent document will be sent with the welcome letter, a second informed consent form will be mailed to the caregiver within one week of the interview if they request. The consent form will have contact information for both the study PI and the Brown University IRB if they have any questions or concerns. Because interviews will be conducted by telephone rather than in-person, we will seek a waiver of documentation of informed consent for the caregiver interviews, as well.

2. Facilitate Understanding

Telephone Interviews with Participants: A trained co-investigator on the research team ([name] [name], and/or [name]) will assess the participant's ability to understand and to express a reasoned choice concerning the purpose of the study and the information relevant to their participation and consequences of participation for the subject's own situation. [name], [name], and/or [name] will determine if all of the following standards are met: Did the participant "make a clear choice"? Did the participant show "understanding"? Did the participant show "reasoning/rational reasons"? Did the participant show an appreciation of the personal risks/benefits of participation in the study? This determination will be accomplished through a four-item informed consent understanding checklist included as an attachment. For individuals who do not pass the 4-item consent capacity checklist, they will be informed that they are ineligible to participate in the interviews. If this event occurs, [name], [name], or [name] will allow as much time as needed to allow the expression of any concerns. While [name], [name], and [name] have years of experience conducting research interviews, including vulnerable populations such as those experiencing cognitive impairment, they will receive training on ensuring understanding by [name], a geriatric psychologist with extensive research experience consenting and interviewing individuals with dementia and their caregivers. In addition, [name] and the PI will regularly meet with [name], [name], and [name] to review their responses on the consent understanding checklist, answer any questions, and discuss any challenges.

Telephone Interviews with Caregivers: A trained research team member will conduct the informed consent process with the Caregiver. There is no reason to believe that the Caregiver will experience any challenges comprehending the informed consent form as they are the person listed as the emergency contact for the MOW participant. Therefore, the research team member will assess the Caregiver's understanding of the consent process through encouraging them to ask questions during the review of the consent form. [name] and the PI will regularly meet with the research team member conducting the interviews and consent process to answer any questions and discuss any challenges.

3. Documentation

Please see below for a request for a waiver of documentation of informed consent for interviews.

4. Additional Considerations

We request a waiver of documentation of informed consent for the telephone interviews with caregivers and participants. We believe that we meet the criteria for a waiver as described in 45 CFR 46.117(c)(ii):

The research presents no more than minimal risk of harm to subjects and involves no procedures for which written consent is normally required outside of the research context.

The interviews will be conducted over the phone and ask minimal risk questions where we anticipate little to no distress as a result of the interviews. Consent would not normally be required for a telephone conversation of this nature, and it would not be practicable to obtain signatures because the interviews are being conducted over the telephone. We request a waiver of informed consent for initial enrollment to be randomized to receive one of the Two types of meals (meals delivered by the MOW programs multiple times a week vs frozen, mailed meals). We believe enrollment in the two types of meal deliveries and analysis using routinely collected data meets the five criteria for a waiver as described in 45 CFR §46.116 f 3 (i-v)and below:

- (i) *The research involves no more than minimal risk to the subjects;*

Our study proposes to provide meals via the two predominant modes of meal delivery currently used by home-delivered meals programs and contracted for by healthcare entities to food insecure, homebound, community-dwelling older adults with ADRD. Because we are recruiting from an existing MOW waitlist, these individuals have already expressed a desire to receive meals and shared their information with MOW, but they are not currently receiving meals because of limitations in program capacity (i.e., inadequate funding to meet demand for meals). The primary outcome analysis for the trial is through secondary data analysis of routinely collected administrative data; therefore, no additional data collection is required or burden will be placed on the enrolled sample. Enrollment and receipt of meals puts these individuals at no greater risk than everyday life.

(ii) The research could not practicably be carried out without the requested waiver or alteration;

Because we are interested in understanding the impact of receiving meals on the time spent in the community among individuals living with dementia, we need to enroll individuals with varying levels of dementia severity. While some individuals with dementia may retain capacity to consent to research (a diagnosis, especially a self-reported diagnosis one, is not determinative), restricting the study to only those able to provide consent would limit the generalizability of our findings, as we would likely only be able to enroll those with less-severe ADRD. If we were to conduct a capacity assessment and sought to include people who lacked capacity to consent to research, we would need to identify a legally authorized representative (LAR). Most individuals with ADRD living in the community do not have a LAR appointed. Some studies have found rates as low as 0% of individuals with mild dementia and only 11-23% of those with moderate to severe dementia have legal documents in place such as guardianship, trusteeship, proxy, or power of attorney (Ruggieri & Piccoli, 2003). Furthermore, LAR rates vary by race and socioeconomic status and are lowest among racial minorities and those with less education (AARP, 2000). Our prior work has found that MOW clients are more likely to be racial and ethnic minorities and low-income than the general population of older adults. In addition, MOW programs do not collect information about clients' LARs. Therefore, there is no mechanism for identifying LARs for potential participants in this study. Finally, MOW programs do not collect information to identify possible surrogates for consent. In addition, surrogate consent laws for research participation vary by state, and it would not be possible to identify a consent process that is consistent across the programs that will participate in the follow-on pragmatic trial and located

in 5 states. Taken together, requiring consent would result in bias through differential selection into the study and comprise the validity and overall scientific value of the study findings.

